3.2 Rationale for Dose, Population, and Endpoints

3.2.1 Dose Rationale

Based on PK/pharmacodynamic (PD) modeling conducted using available clinical literature data on GLP-1 and glucagon receptor modulators, the clinically efficacious dose of

[figure not shown]
MEDI0382 was predicted to be in the range of 300 to 2000 µg/day; however, clinical data from Study D5670C00001 identified dose-limiting tolerability issues (multiple episodes of vomiting) at the 300 µg dose administered as a single dose without initial up-titration. The principle of dose up-titration to achieve greater tolerability at higher than initial doses was well established with daily GLP-1 agents ([Victoza, 2016](#)). Studies of other GLP-1 receptor agonists suggest that the maximal dose response with respect to weight loss may be seen at higher doses in comparison to those at which maximal reduction in blood glucose is achieved ([Davies et al, 2015](#); [Nauck and Marre, 2009](#)). This is particularly true of GLP-1/glucagon dual agonists where the glucagon agonist component is likely to drive incremental weight loss over time, and confer accompanying improvements in glycemic control ([Henderson et al, 2016](#)).

This study is designed to explore both the appropriate dose titration schedule for repeated doses of MEDI0382 and the highest clinically tolerated repeat-dose in subjects with T2DM. Therefore, the proposed dose range allows characterization of the safety/tolerability profile of MEDI0382 at a relevant pharmacological range and facilitates design of future studies.

The no-observed-adverse-effect-level (NOAEL) of 90 µg/kg/day was based on findings in the 9-month, daily repeat dose SC toxicology study in the cynomolgus monkey. These were considered to be consistent with pharmacology-mediated induction of weight loss/lower weight gain, reversible changes in the pancreas (acinar degranulation and hypercellularity of the pancreatic islets), and changes in energy utilization and associated metabolic stress (minor changes in blood chemistry parameters, lower thymus weights). Treatment was also associated with changes in the skin (dermal irritation, acanthosis and hyperkeratosis) in 3 of 4 female cynomolgus monkeys dosed.

While the NOAEL determined in the rat 6-month, daily repeat dose SC toxicology study (ie, 7.5 µg/kg/day) was lower than that in the cynomolgus monkey, this was driven primarily by the findings in the thyroid gland (C-cell hyperplasia, adenoma, and carcinoma) that were considered, in this species, to be adverse. This is a known class effect with GLP-1 receptor agonists that is considered rodent specific and of unknown relevance to humans ([Center for Drug Evaluation and Research, 2005](#)). Therefore cynomolgus monkey, and the toxicity profile of MEDI0382 generated in that species, are considered to be the most appropriate non-clinical species to use for clinical risk assessment and the setting of safety margins.

3.2.2 Rationale for Study Population

MEDI0382 is a synthetic oxyntomodulin-like peptide with targeted GLP-1 and glucagon receptor activity, which relies upon glucose-dependent insulin release (the incretin effect) for glucose lowering efficacy, and is therefore targeted at subjects with T2DM.

Adult subjects with T2DM who are overweight or obese are likely to benefit most from losing weight. While subjects with a BMI > 40 kg/m², or > 35 kg/m² with 1 or more obesity-related comorbidity may be offered bariatric surgery, those with a BMI in the range of 27-35 kg/m² rely upon conservative or medical management for weight reduction. The entry criteria with respect to T2DM and BMI of 27-35 kg/m² creates a more homogeneous population than has been studied previously, limiting the potential effect of exposure on tolerability, while generating safety, and tolerability data in the likely intended clinical population.

3.2.3 Rationale for Endpoint(s)

3.2.3.1 Primary Endpoint

In a previous study (D5670C00002), repeat doses of MEDI0382 ≤ [REDACTED] have been shown to have an acceptable tolerability and safety profile. However, this study is the first to explore higher doses of MEDI0382 [REDACTED] in the T2DM population. Therefore, it is appropriate that safety and tolerability represent the primary endpoint. Safety and tolerability will be measured with safety laboratory tests, physical examination, ABPM recording of heart rate and BP, ECG and other vital signs, and recording of AEs.

3.2.3.2 Secondary Endpoints

Pharmacokinetic and Immunogenicity Profile

Plasma concentrations of MEDI0382 will be used to evaluate the PK profile (C_{max} , time to maximum observed concentration [T_{max}], AUC_{tau}). In addition, trough plasma concentrations (C_{trough}) will be evaluated to establish accumulation ratio and explore PK linearity.

Anti-drug antibody (ADA) incidence rate and titer will be tabulated for each treatment to monitor immunogenicity. Samples confirmed positive for ADA will be tested and analyzed for antibody titer and reported.

[REDACTED]

[REDACTED]

Body Weight

Prior experience with MEDI0382 has demonstrated a weight-lowering effect at doses $\leq 300 \mu\text{g}$ (Ambery et al, 2018). Therefore, percentage and absolute change in weight and the proportion of subjects achieving clinically significant weight loss ($> 5\%$ of body weight) will be recorded to document the effect of MEDI0382 on body weight at higher doses than previously studied [REDACTED]

[REDACTED]

4 MATERIALS AND METHODS

4.1 Subjects

4.1.1 Number of Subjects

Up to 20 subjects will be randomized in 2 cohorts: 8 subjects in Cohort 1 and 12 subjects in Cohort 2.

4.1.2 Inclusion Criteria

Subjects must meet all of the following criteria:

- 1 Subjects aged 18 to 74 years (inclusive) at screening
- 2 Provision of signed and dated written informed consent (with the exception of consent for genetic and non-genetic research) prior to any study specific procedures
- 3 BMI between 27 and 35 kg/m² (inclusive) at screening
- 4 HbA1c range of 6.5% to 8.5% (inclusive) at screening (Note: Subjects may be re-tested for the HbA1c entry criterion only once.)
- 5 Willing and able to self-inject investigational product for the duration of the study
- 6 Diagnosed with T2DM with glucose control managed with metformin monotherapy where no significant dose change (increase or decrease \geq 500 mg/day) has occurred in the three months prior to screening. For inclusion into Cohort 2 only, subjects prescribed oral dual therapy with a dipeptidyl peptidase-4 inhibitor, sulphonylurea, glitinide, or a sodium-glucose co-transporter 2 inhibitor in addition to metformin at screening may be eligible to enter the study following a 4-week washout period. Following wash-out, the subject must re-attend for fasting plasma glucose and HbA1c measurement to confirm eligibility prior to run-in. At this visit, an HbA1c of between 6.5% to 8.5%, inclusive **and** fasting plasma glucose level < 225 mg/dL (< 13.0 mmol/L) is acceptable. If the subject fails to meet these criteria, one repeat measurement is allowed on a different day prior to Day -10.
- 7 Female subjects must have a negative pregnancy test at screening and randomization, and must not be lactating.
- 8 Female subjects of childbearing potential who are sexually active with a male partner must be using at least one highly effective method of contraception (see [Appendix A](#) for definition of females of childbearing potential and for a description of highly effective methods of contraception) from screening and up to 4 weeks after the last dose of

investigational product. It is strongly recommended for the male partner of a female subject to also use male condom plus spermicide throughout this period. Cessation of contraception after this point should be discussed with a responsible physician. Periodic abstinence, the rhythm method, and the withdrawal method are not acceptable methods of contraception.

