3.1.4 Management of Study Medication Related Toxicities

GI Tolerability

In this study, dose escalation may be limited by GI tolerability, specifically with respect to nausea and vomiting

Prior to receiving investigational product, subjects will be advised that transient nausea and vomiting are possible and will receive counseling about meal size and eating habits. Specifically, subjects will be advised to avoid administering the medication close to a large or high-fat meal; to consume small, frequent meals 4 to 5 times a day that are low in fat and insoluble fibers; and to stop eating when they are feeling full. Subjects will also be advised to avoid carbonated beverages, alcohol, and smoking to help prevent the occurrence of nausea and vomiting. This advice should be reiterated should symptoms of nausea and vomiting occur once investigational product dosing has initiated. If symptoms do not improve despite a change of dietary habits, metformin may be withheld for 3 days, or alternatively, subjects should be offered antiemetic therapy in accordance with institutional and local practice guidelines. A centrally acting antiemetic such as a 5HT-3 antagonist (eg, ondansetron) or cyclizine is the preferred treatment in the first instance, rather than a prokinetic agent such as domperidone or metoclopramide.

Hyperglycemia

In the unlikely event of suspected persistent hyperglycemia in a subject based on either symptoms of hyperglycemia (eg, thirst, polyuria, blurred vision), capillary blood glucose readings (eg, 3 readings > 260 mg/dL [14.4 mmol/L] within one week), the investigator should perform additional fasting blood glucose levels as necessary to further investigate, and subjects should be asked to monitor capillary plasma glucose levels up to 5 times per day. If 2 or more laboratory plasma fasting glucose levels of > 260 mg/dL [14.4 mmol/L] taken at least 3 days apart are detected, the subject should be discontinued from the study (Section 4.1.6), and rescue therapy should be considered in line with current local guidelines.

Hypoglycemia

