Any blood glucose level 54 mg/dL (< 3.0 mmol/L) with or without symptoms is considered as clinically significant hypoglycemia and should be reported by the Investigator as an AE. Spontaneous and clinically significant hypoglycemia has not been observed in prior studies with MEDI0382 up to a dose of 300 µg alongside metformin treatment. All subjects will be provided with a glucometer and will be advised to check their capillary blood glucose level if they have symptoms of hypoglycemia (hunger, dizziness, shaking, sweating, or irritability) or feel unwell. Any such subjects should be managed using local protocols for treatment and follow-up of any hypoglycemic episode. Pharmacological treatments administered for hypoglycemia, eg, dextrose/glucose tablets, glucose infusion, glucagon injection etc, should be recorded in the electronic case report form (eCRF) as concomitant medications.

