4.1.6 Discontinuation of Investigational Product

An **individual subject** will not receive any further investigational product if any of the following occur in the subject in question:

- 1 Withdrawal of consent from further treatment with investigational product
- 2 Lost to follow-up
- 3 An AE that, in the opinion of the investigator or the sponsor, warrants discontinuation of further dosing
- 4 Pregnancy in a female subject (see Section 5.6.2 for additional details regarding pregnancy)
- 5 Signs or symptoms of severe hepatic impairment including abnormal laboratory values according to below:
 - (a) ALT and/or AST are $> 3 \times \text{ULN}$ and TBL $> 2 \times \text{ULN}$
 - (b) ALT and/or AST are $> 5 \times \text{ULN}$ for ≥ 14 consecutive days, at any time after initial confirmatory results
 - (c) ALT and/or AST are $> 8 \times \text{ULN}$
- 6 Average absolute (regardless of baseline value) cardiac QTc interval corrected for heart rate by QTcF > 500 msec, or an increase of QTcF > 60 msec above the baseline value, confirmed (persistent for ≥ 5 minutes) on a repeat 12-lead ECG
- 7 Any one of the following:
 - (a) **Tachycardia**, defined as resting supine pulse rate > 125 beats per minute persisting for at least 10 minutes
 - (b) **Symptomatic bradycardia**, defined as resting supine pulse rate < 40 beats per minute while awake, persisting for at least 10 minutes
 - (c) **Asymptomatic bradycardia**, defined as resting supine pulse rate < 30 beats per minute while awake persisting for at least 10 minutes
 - (d) **Hypertension**, defined as an increase from baseline in resting supine systolic > 40 mmHg or above 180 mmHg and persisting for at least 10 minutes and/or increase from baseline in resting supine diastolic BP > 20 mmHg or above 100 mmHg and persisting for at least 10 minutes
- 8 Persistent hyperglycemia detected as 2 or more laboratory plasma fasting glucose levels of > 260 mg/dL (14.4 mmol/L) taken at least 3 days apart are detected

Subjects who are permanently discontinued from receiving investigational product will be followed for protocol-specified assessments including the 28-day post-last-dose safety follow-up visit and continued follow-up of any AEs unless consent is withdrawn from further study participation, the subject is lost to follow-up, the subject starts alternative treatment, or the subject is enrolled in another clinical study.

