 - ^e BP and heart rate should be measured once at heart level in the non-dominant arm where possible, with the subject supine for 10 minutes prior to the measurement (rest period for ECG will suffice).
 - ^f HbA1C to be re-checked prior to the start of the run-in period only for those subjects washing out from a second anti-hyperglycemic agent
 - ^g **Fasting** plasma glucose to be checked prior to the start of the run-in period for those subjects washing out from a second anti-hyperglycemic agent
 - ^h An alcohol breath test is an acceptable alternative to an alcohol urine test.
 - ⁱ Subjects should be shown the device and given an explanation as to how it is worn.
 - ^j Subject's ability to administer a SC injection will be verified by undergoing a single SC injection using normal saline provided by the site. Willingness to perform this for the duration of the study should be discussed with the subject. Further training may be given during the run-in period as required.
 - ^k Subjects will be fitted with the ABPM device while at the clinical unit, which may involve practice inflations. The subject will then wear the monitor/cuff for approximately 24 hours (including overnight at home) and will remove the device at home at the end of the 24-hour period.
 - ^l [REDACTED]
 - ^m FSH should only be checked in female subjects who are post-menopausal and have no previous confirmatory laboratory FSH result available.
- # Collection of Informed consent may occur prior to the other screening assessments, on a separate visit if required

[figure not shown]
[REDACTED]

[figure not shown]
[REDACTED]

[REDACTED]

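### Inclusion criterion 6 gives one fasting glucose limit in two units that disagree: 225 mg/dL is 12.5 mmol/L, not 13.0 mmol/L

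*Protocol*

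**What the plan says.** Protocol 4.1.2, criterion 6, admits subjects on metformin alone. It then opens a second route: "For inclusion into Cohort 2 only, subjects prescribed oral dual therapy" may enter after a 4-week washout. These subjects come back before run-in and must meet two conditions together: HbA1c of 6.5% to 8.5%, and a "fasting plasma glucose level < 225 mg/dL (< 13.0 mmol/L) is acceptable".

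A failure may be retested once: "If the subject fails to meet these criteria, one repeat measurement is allowed on a different day prior to Day -10". Table 5, footnote g (Protocol 4.2.1) schedules the measurement, with fasting "plasma glucose to be checked prior to the start of the run-in period for those subjects washing out from a second anti-hyperglycemic agent".

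The protocol prints glucose thresholds in both units in three other places:

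- Section 3.1.4, Hyperglycemia: "260 mg/dL [14.4 mmol/L] taken at least 3 days apart".
- Section 4.1.6, item 8: "260 mg/dL (14.4 mmol/L) taken at least 3 days apart".
- Section 3.1.4, Hypoglycemia: "Any blood glucose level 54 mg/dL (< 3.0 mmol/L) with or without symptoms".

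The SAP does not restate the entry limit. Nothing in either document corrects the 225/13.0 pair or says which unit takes precedence.

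**The concern.** The bracketed figure reads as the same limit in other units, as it does in the protocol's other glucose thresholds. Here it is a different limit. The criterion is pass/fail, so for a subject between the two figures the answer depends on which one the site reads. Four things follow from that choice:

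- whether the repeat test is needed, and whether it is passed;
- whether the subject may be randomized;
- whether the medical monitor has to be told that an ineligible subject was randomized and treated (Protocol 4.1.4);
- whether the case could belong in the listing of important protocol deviations (SAP 3.8).

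The repeat test does not resolve the conflict, because it is judged against the same two figures.

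**Working it through.** **Inputs.** The printed pairs are 225 mg/dL with 13.0 mmol/L (Protocol 4.1.2), 260 with 14.4 (3.1.4 and 4.1.6) and 54 with 3.0 (3.1.4). The conversion factor is not in the documents. I take 18.016 mg/dL per mmol/L, from a molar mass for glucose of about 180.16 g/mol, and check it against the protocol's own pairs.

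**Step 1: try to reproduce the plan's figure.**

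- 225 / 18.016 = 12.49 mmol/L, which rounds to 12.5. The protocol prints 13.0.
- In the other direction, 13.0 × 18.016 = 234.2 mg/dL. The protocol prints 225.
- Gap: 234.2 − 225 = 9.2 mg/dL, or 13.0 − 12.49 = 0.51 mmol/L. Relative to the lower limit, 9.2 / 225 = 4.1%.

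**Step 2: check the factor on the other pairs.**

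- 260 / 18.016 = 14.43, printed as 14.4: correct.
- 54 / 18.016 = 3.00, printed as 3.0: correct.

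**Step 3: compare implied factors (mg/dL divided by mmol/L).** The range allows for rounding of the mmol/L figure to one decimal.

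| Pair | Implied factor | Range |
|---|---|---|
| 260 / 14.4 | 18.06 | 17.99 to 18.12 |
| 54 / 3.0 | 18.00 | 17.70 to 18.31 |
| 225 / 13.0 | 17.31 | 17.24 to 17.37 |

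The criterion 6 range does not overlap either of the others.

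**Step 4: test rounding directly.** A limit that rounds to 13.0 mmol/L lies from 12.95 × 18.016 = 233.3 to 13.05 × 18.016 = 235.1 mg/dL, which excludes 225. A limit that rounds to 225 mg/dL lies from 224.5 / 18.016 = 12.46 to 225.5 / 18.016 = 12.52 mmol/L, which excludes 13.0.

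**Step 5: repeat without any outside factor.**

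- With the 260/14.4 pair: 225 × 14.4 / 260 = 12.46 mmol/L, and 13.0 × 260 / 14.4 = 234.7 mg/dL.
- With the 54/3.0 pair: 225 × 3.0 / 54 = 12.50 mmol/L, and 13.0 × 54 / 3.0 = 234.0 mg/dL.

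**Example.** A subject at 230 mg/dL has 230 / 18.016 = 12.8 mmol/L. This fails the mg/dL limit and passes the mmol/L limit.

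**The case against.** The arithmetic is not in dispute. The case on the other side is about weight.

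- *This is a clerical slip with little behind it.* Both candidate limits, 225 and 234 mg/dL, lie well below the 260 mg/dL discontinuation threshold, so neither conflicts with the on-study glucose safety rule. The SAP has no per-protocol population (SAP 3.2), so a treated subject from the disputed band stays in the As-treated and ITT sets. The stopping criteria and the efficacy models do not use the limit. All of this stands, and it is why the point is minor.
- *A site will read the figure in its laboratory's unit.* Safety tests run in a licensed local laboratory (Protocol 4.3.3), so decisions at one site may well be consistent. That is plausible, but the documents do not state the reporting unit, and consistent use of one figure does not show that it is the intended one.
- *The protocol rounds unit pairs elsewhere.* Exclusion criterion 7 (Protocol 4.1.3) pairs 11 mmol/L of triglycerides with 1000 mg/dL. Assuming about 88.6 mg/dL per mmol/L, 1000 / 88.6 = 11.3, which rounds to the printed whole number. The glucose limit carries a decimal. It is possible that 12.5 was rounded up to 13 and the decimal added later, but the printed limit is still 13.0.
- *The hypoglycemia pair is not a clean comparator.* It lacks a less-than sign on the mg/dL side. That is true, but its two numbers still convert correctly, and the 260/14.4 pair is enough by itself.

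**Conclusion.** The inconsistency is real: criterion 6 states two different limits, 12.5 and 13.0 mmol/L (225 and 234 mg/dL). Rounding does not reconcile them, and the result holds on the protocol's own conversions as well as on the standard factor.

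The severity is minor. The only people affected are candidates for Cohort 2 who wash out a second oral agent, have HbA1c in range, and fall in a band about 9 mg/dL wide. Among randomized subjects that is at most the 12 in Cohort 2. The limit acts before run-in, so people turned away on the stricter figure would come on top of that. The documents give neither the number screened nor the expected number of washout subjects, so no likely count can be stated. Nor do they show which of the two figures was intended.

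**What to change.** Decide which limit was meant and correct the other figure in criterion 6. Either keep 225 mg/dL and change the bracket to 12.5 mmol/L, or keep 13.0 mmol/L and change the first figure to 234 mg/dL. If washout subjects have already been screened, check whether any had a post-washout fasting glucose between the two limits, and record which figure was applied.

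The cost is one number in the protocol text. Design, sample size, SAP and analyses do not change. Amendment 2 made corrections of the same kind in this section (Protocol 9.2).

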4.1.3 Exclusion Criteria

- 1 History of, or any existing condition that, in the opinion of the investigator, would interfere with evaluation of the investigational product, put the subject at risk, influence the subject's ability to participate or affect the interpretation of the results of the study and/or any subject unable or unwilling to follow study procedures during the run-in period
- 2 Any subject who has received another investigational product as part of a clinical study or a GLP-1 analogue containing preparation within the last 30 days or 5 half-lives of the drug (whichever is longer) at the time of screening
- 3 Concurrent participation in another study of any kind and repeat randomization in this study is prohibited
- 4 Any subject who has received any of the following medications within the specified timeframe prior to the start of the study (see Section 4.7.2 for further details)
 - Herbal preparations within one week prior to the start of dosing or drugs licensed for control of body weight or appetite (eg, orlistat, bupropion-naltrexone, phentermine-topiramate, phentermine, lorcaserin) within 30 days (or 5 half-lives of the drug) prior to the start of dosing
 - Opiates, domperidone, metoclopramide, or other drugs known to alter gastric emptying and within 2 weeks prior to the start of dosing
 - Antimicrobials within the quinolone (eg, ciprofloxacin), macrolide (eg, clarithromycin) or azole class (eg, ketoconazole) within 2 weeks prior to the start of dosing
 - Any change in antihypertensive medication within 3 months prior to screening
 - Aspirin (acetylsalicylic acid) at a dose greater than 150 mg once daily
 - Paracetamol (acetaminophen) or paracetamol-containing preparations at a total daily dose of greater than 3000 mg
 - Ascorbic acid (vitamin C) supplements at a total daily dose of greater than 1000 mg
- 5 Severe allergy/hypersensitivity to any of the proposed study treatments, standardized meals, or excipients
- 6 Symptoms of acutely decompensated blood glucose control (eg, thirst, polyuria, weight loss), a history of type 1 diabetes mellitus or diabetic ketoacidosis, or if the subject has been treated with daily SC insulin within 90 days prior to screening
- 7 Acute pancreatitis, pancreatic amylase, and/or pancreatic lipase $> 3 \times$ ULN; history of chronic pancreatitis; or serum triglyceride levels > 11 mmol/L (1000 mg/dL) at screening
- 8 Significant inflammatory bowel disease, gastroparesis or other severe disease or surgery affecting the upper GI tract (including weight-reducing surgery and procedures), which

- may affect gastric emptying or could affect the interpretation of safety and tolerability data
- 9 Significant hepatic disease (except for NASH or non-alcoholic fatty liver disease without portal hypertension or cirrhosis) and/or subjects with any of the following results at screening:
 - Aspartate transaminase (AST) $\geq 3 \times$ upper limit of normal (ULN)
 - Alanine transaminase (ALT) $\geq 3 \times$ ULN
 - Total bilirubin (TBL) $\geq 2 \times$ ULN
 - 10 Impaired renal function defined as estimated glomerular filtration rate (GFR) < 60 mL/minute/1.73m² at screening (GFR estimated according to Modification of Diet in Renal Disease (MDRD) using MDRD Study Equation IDMS-traceable [SI units]).
 - 11 Poorly controlled hypertension defined as:
 - Systolic BP > 160 mmHg
 - Diastolic BP or ≥ 90 mmHgAfter 10 minutes of supine rest and confirmed by repeated measurement at screening. Subjects who fail BP screening criteria may be considered for 24-hour ABPM at the discretion of the investigator. Subjects who maintain a mean 24-hour BP $< 160/100$ mmHg with a preserved nocturnal dip of $> 15\%$ will be considered eligible.
 - 12 Any clinically important abnormalities in rhythm, conduction, or morphology of the resting 12-lead ECG or any abnormalities that may interfere with the interpretation of serial ECG changes, including corrected QT (QTc) interval changes at screening, as judged by the investigator
 - 13 Prolonged QT intervals corrected for heart rate using Fridericia's formula (QTcF) > 450 ms, or family history of long QT-segment at screening
 - 14 PR (PQ) interval prolongation (> 220 msec), intermittent second (Wenckebach block while asleep is not exclusive), or third-degree atrioventricular (AV) block, or AV dissociation
 - 15 Persistent or intermittent complete bundle branch block. Subjects with QRS > 110 msec but < 115 msec are acceptable if there is no evidence of ventricular hypertrophy or pre-excitation
 - 16 Unstable angina pectoris, myocardial infarction, transient ischemic attack, or stroke within 3 months prior to screening, or subjects who have undergone percutaneous coronary intervention or a coronary artery bypass graft within the past 6 months or who are due to undergo these procedures at the time of screening
 - 17 Severe congestive heart failure (New York Heart Association Class III or IV)
 - 18 Basal calcitonin level > 50 ng/L at screening or history/family history of medullary thyroid carcinoma or multiple endocrine neoplasia
 - 19 Hemoglobinopathy, hemolytic anemia or chronic anemia (hemoglobin, < 11.5 g/dL [115 g/L] for males, < 10.5 g/dL (105 g/L) for females) at screening or any other condition known to interfere with the interpretation of HbA1c measurement
 - 20 History of neoplastic disease within 5 years prior to screening, except for adequately treated basal cell, squamous cell skin cancer, or in situ cervical cancer

- 21 Any positive results for serum hepatitis B surface antigen, hepatitis C antibody, and human immunodeficiency virus (HIV) antibody
- 22 History of substance dependence, alcohol abuse, or excessive alcohol intake (defined as an average daily intake of > 24 g for men or > 12 g women) within 3 years prior to screening and/or a positive screen for drugs of abuse or alcohol at screening or on admission to the study unit. Subjects who use benzodiazepines for chronic anxiety or sleep disorders may be permitted to enter the study.
- 23 Symptoms of depression or any other psychiatric disorder requiring treatment with medication (eg, anti-depressants, anti-psychotics) at screening. However, subjects who use benzodiazepines for chronic anxiety or sleep disorders may be permitted to enter the study.
- 24 History of severe allergy/hypersensitivity, including to any component of the investigational product formulation or other biological agent, or ongoing clinically important allergy/hypersensitivity as judged by the investigator
- 25 Blood/plasma donation within 1 month of screening
- 26 Involvement of any AstraZeneca, MedImmune, the contract research organization, or the virtual study site employee or their close relatives

Subjects may be rescreened once if in the opinion of the investigator there is a reason to believe they may be eligible.

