3.1.3.2 Dose Escalation Stopping Criteria

Dose escalation will be stopped if the DEC determines that any of the following criteria are met.

- More than 50% of subjects treated with MEDI0382 in a specific dose period experience grade 2 or higher AEs assessed as related to MEDI0382 and require discontinuation of MEDI0382
- One serious adverse event (SAE) occurs in a MEDI0382 subject that is assessed as related to MEDI0382
- Two or more subjects receiving MEDI0382 experiences any of the following:
 - An average absolute (regardless of baseline value) cardiac QTc interval corrected for heart rate by the formula of Fridericia (QTcF) > 500 msec, or an increase of QTcF > 60 msec above the baseline value, confirmed (persistent for ≥ 5 minutes) on a repeat 12-lead ECG
 - Tachycardia, defined as resting supine heart rate > 125 beats per minute persisting for at least 10 minutes (measured at 5 timepoints in the 10-minute period)
 - Symptomatic bradycardia, defined as resting supine heart rate < 40 beats per minute while awake, persisting for at least 10 minutes; or asymptomatic bradycardia defined as resting supine heart rate < 30 beats per minute while awake persisting for at least 10 minutes (measured at 5 timepoints in the 10-minute period)
 - Hypertension, defined as an increase from baseline in resting supine systolic blood pressure (BP) > 40 mmHg or above 180 mmHg and persisting for at least 10 minutes, or an increase from baseline in resting supine diastolic BP > 20 mmHg or above 100 mmHg and persisting for at least 10 minutes
- The above cardiac criteria do not apply if provoked by complicated venepuncture or other vagal provocation

If any of these criteria are met, then the DEC will either:

- Recommend that the study proceed to 3-week treatment extension at the HCTD, or
- Request for review and decision by the MedImmune Safety Review Board on how to proceed or whether to suspend or stop the study

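### Exclusion 11 admits subjects through ambulatory BP with no ceiling on clinic BP, so entry can overlap the diastolic limit for discontinuation and the escalation stop

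*Protocol*

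**What the plan says.** **Entry.** Protocol 4.1.3, criterion 11, defines poorly controlled hypertension by a supine clinic reading after 10 minutes of rest, confirmed by repeat at screening. The limits are "Systolic BP > 160 mmHg" and a diastolic of 90 mmHg or more. A subject who fails has another way in: "Subjects who fail BP screening criteria may be considered for 24-hour ABPM at the discretion of the investigator". The subject is then eligible if the 24-hour mean is below 160/100 mmHg and the nocturnal dip exceeds 15%. No upper limit on the clinic reading is attached to this route.

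**Individual discontinuation.** Section 4.1.6, item 7(d), bars further product for "an increase from baseline in resting supine systolic > 40 mmHg or above 180 mmHg and persisting for at least 10 minutes", with a matching diastolic limb of a rise above 20 mmHg or a level above 100 mmHg.

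**Escalation stop.** Section 3.1.3.2 uses the same figures, the diastolic limb being "an increase from baseline in resting supine diastolic BP > 20 mmHg or above 100 mmHg and persisting for at least 10 minutes". It applies when "Two or more subjects receiving MEDI0382 experiences any of the following", the list being QTcF, tachycardia, bradycardia and hypertension. The one stated exception is "The above cardiac criteria do not apply if provoked by complicated venepuncture or other vagal provocation".

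In both sections the QTcF criterion says explicitly that its absolute limit applies whatever the baseline. The BP criterion says nothing either way.

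**The concern.** Entry by the ABPM route is judged on an ambulatory mean. Discontinuation and the escalation stop are judged on resting supine clinic BP. The two are not tied together, and the ambulatory diastolic limit for entry (100) is looser than the clinic limit that the subject has just failed (90). Someone can therefore be randomised while already above, or barely below, the clinic diastolic level at which they must stop treatment.

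Other paired limits in the protocol leave room or do not cross. QTcF excludes above 450 msec and stops above 500. Fasting glucose after washout must be below 225 mg/dL, and discontinuation needs values above 260. AST or ALT of 3 times ULN or more, or bilirubin of 2 times ULN or more, excludes; the combined liver rule stops only above those levels.

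Two things are at stake. A subject could be dosed and then taken off treatment for BP that was there beforehand. If that subject is on MEDI0382, the event could also be one of the two needed for the escalation stop, which bears on the HCTD. Section 1.6 lists altered BP as a potential risk of MEDI0382, so this is a signal that the trial needs to read cleanly.

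**Working it through.** The plan gives no figure to reproduce here; N = 20 is described as empirical. The check compares the limits and then asks how readily they overlap.

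**1. Limits side by side (mmHg)**

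| Place | Measurement | Diastolic | Systolic |
|---|---|---|---|
| 4.1.3 no. 11, clinic route | supine, confirmed | excluded at 90 or more | excluded above 160 |
| 4.1.3 no. 11, ABPM route | 24-hour mean, dip above 15% | eligible below 100 | eligible below 160 |
| 4.1.6 item 7(d) | resting supine, 10 min | rise above 20, or level above 100 | rise above 40, or level above 180 |
| 3.1.3.2, two MEDI0382 subjects | resting supine, 10 min | same | same |

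Rise in clinic diastolic needed to exceed 100:
- from 89, the highest whole number passing directly: more than 100 − 89 = 11
- from 99 (ABPM route only): more than 100 − 99 = 1
- from 101 (ABPM route only): none, since 100 − 101 is negative

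**2. Does the ABPM limit itself admit daytime values above 100?**
With 24-hour mean M, S hours asleep and dip d, the awake mean is M / f, where f = [(24 − S) + S(1 − d)] / 24. Take M = 99.9 and d = 0.15. S is an assumption.
- S = 6: f = 23.1/24 = 0.9625; awake mean 103.8
- S = 8: f = 22.8/24 = 0.950; awake mean 105.2
- S = 9: f = 22.65/24 = 0.94375; awake mean 105.9

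At 8 hours the awake mean passes 100 once the 24-hour mean passes 100 × 0.95 = 95. A larger dip raises the awake mean further. If the mean is instead the plain average of all readings (Section 4.3.2.4: every 15 minutes by day, every 30 overnight), 8 hours asleep gives 64 day and 16 night readings. Then f = 0.8 + 0.2 × 0.85 = 0.97 and the awake mean is 103.0, still above 100.

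The awake mean is not the resting supine reading, but this shows that the overlap does not depend on a white-coat effect.

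**3. Systolic**
With M = 159.9 the awake mean is 166.1 (6 h), 168.3 (8 h) or 169.4 (9 h). To exceed 180 at the clinic, the clinic reading must be above the awake mean by more than 180 − 169.4 = 10.6 to 180 − 166.1 = 13.9, and above the 24-hour mean by more than 20. The text permits this, but it is less likely than the diastolic overlap.

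**4. Two-subject rule, Cohort 1 (3:1 in 8 gives 6 MEDI0382, 2 placebo)**
- If exactly two such subjects are among the 8: P(both on MEDI0382) = C(6,2)/C(8,2) = 15/28 = 54%.
- If one of the 6 on MEDI0382 is already counted, and each of the other 5 independently meets any listed criterion with assumed probability p, P(rule met) = 1 − (1 − p)^5, against P(2 or more of 6) without that subject. At p = 5%: 22.6% against 3.3%. Over p = 2% to 20%: 9.6% to 67.2% against 0.6% to 34.5%.
- If each MEDI0382 subject independently has an assumed 1%, 2% or 5% chance of being such an entrant, P(2 or more of 6) is 0.15%, 0.6% or 3.3%.

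**The case against.** The strongest case against is that the overlap is rare and that people stand between it and any consequence.

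- **Filters at entry.** ABPM is at the investigator's discretion, exclusion 1 allows refusal on judgement, vital signs precede the first dose, and ABPM is repeated at run-in and on Day -2. These narrow the route, but none is a numeric ceiling. The pre-dose recheck of eligibility uses the same criteria, which the subject has passed through ABPM.
- **Wording.** The BP limb opens with an increase from baseline, so the absolute level could be read as an increase to above 100. On that reading a stable 104 does not qualify, though a very small rise would. This stands as a real ambiguity and is part of the point.
- **Persistence.** Scheduled BP is measured once, so a routine visit does not by itself show 10 minutes above the limit. The screening failure was, however, itself confirmed after supine rest.
- **The HCTD.** A reader might infer that entry BP would fix the HCTD. The documents do not support that as a direct consequence. The stop applies if the DEC determines that a criterion is met, and the DEC may refer the matter to the Safety Review Board. A subject who meets the limit at the first on-treatment reading leaves at the starting dose, below which there is no level to declare. The event matters later only because the DEC reviews cumulative data. The two-subject rule, unlike the more-than-50% AE rule, is not confined to one dose period.
- **Lost data.** A reader might infer that these subjects' safety data are lost. Section 4.1.6 generally keeps discontinued subjects in follow-up; what is lost is their exposure at higher doses.

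Table 6 and part of 3.1.3 are not visible in the public text, and the DEC charter is a separate document. Handling there cannot be ruled out.

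**Conclusion.** The concern holds for diastolic BP. As written, an eligible subject can be above the diastolic discontinuation limit, or within a trivial rise of it, before the first dose. Nothing in the visible text prevents this or says whether such a level counts. The systolic overlap is possible but needs a large gap between clinic and ambulatory readings.

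The size is uncertain. The documents give no figure for how many subjects would enter through ABPM. The 54% must not be read as the chance of a spurious stop: it assumes exactly two such subjects in Cohort 1 and describes only their allocation. The awake mean of 104 to 106 rests on 6 to 9 hours asleep, a time-weighted mean just under 100 and a dip at the 15% boundary. The effect on escalation runs through the DEC's determination on cumulative data and is not automatic.

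This should be fixed. It is a low-cost inconsistency touching subject safety and a listed risk, but it does not by itself undermine the trial.

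**What to change.** The sponsor should reconcile criterion 11 of 4.1.3, Section 3.1.3.2, item 7(d) of 4.1.6 and the DEC charter, so that the entry, discontinuation and stopping BP criteria do not overlap. The same wording should state how the absolute BP limits relate to the pre-dose baseline, as the QTcF criterion already does. Which values apply, and how a level present before dosing is handled, are for the sponsor to decide.

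The cost is wording in the protocol and charter, and possibly a few ABPM-route subjects no longer eligible. No new measurement is needed.
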